## LIST OF ABBREVIATIONS

ADaM	analysis data model
AE, AR	adverse event(s), adverse reaction(s)
ALT	alanine aminotransferase
APRI	AST to platelet ratio index
AST	aspartate aminotransferase
AUC	area under the curve
BMI	body mass index
BP	blood pressure
CL/F	apparent total clearance after oral administration
C max	maximum concentration
eCRF	electronic case report form
CRO	contract research organization
CS, NCS	clinically significant, non-clinically significant
CV	cardiovascular
CYP450, CYP3A4	cytochrome P450, cytochrome P450 3A4
CYP7A1	cholesterol 7 $\alpha$ -hydroxylase
EC	ethics committee
ECG	electrocardiogram
EOS	end-of-study
EOT	end-of-treatment
F	oral bioavailability
FDA	Food and Drug Administration
FIB-4	fibrosis 4 index
FXR	farnesoid X receptor
GCP, GMP, GLP	good clinical practice, good manufacturing practice, good laboratory practice
HBV	hepatitis B virus
HCV	hepatitis C virus
HDL-C	high density lipoprotein cholesterol
HDPE	high density polyethylene
hERG	human Ether-à-go-go -related gene
HIV	human immunodeficiency virus
HR	heart rate
hs-CRP	high-sensitivity C-reactive protein
HV	healthy volunteers
IB	investigator's brochure
ICF	informed consent form
ICH	International Council on Harmonisation
INR	international normalized ratio
IRB	institutional review board
IU	international units
IUD, IUS	intrauterine device, intrauterine system
IWRS	interactive web response system
MAD	multiple ascending dose
MedDRA	medical dictionary for regulatory activities
NAFL, NAFLD	non-alcoholic fatty liver, non-alcoholic fatty liver disease

NASH	non-alcoholic steatohepatitis
NCI CTCAE	National Cancer Institute, Common Terminology Criteria for Adverse Events
NFS	NAFLD fibrosis score
NOAEL/NOEL	no observed adverse effect level/ no observed effect level
OCA	obeticholic acid
PBC	primary biliary cholangitis
PBC-ANAb	PBC-specific antinuclear antibodies
PD	pharmacodynamics
P-gp	P-glycoprotein
PI	principal investigator
PK	pharmacokinetics
PN	presumptive NAFLD (non-alcoholic fatty liver disease)
po	oral administration (by mouth, per os)
PT/PTT	prothrombin time / partial thromboplastin time
QD	once daily
SAD	single ascending dose
SAE	serious adverse event(s)
SAP	statistical analysis plan
SHP	small heterodimer partner
SOC	system organ class
SUSAR	suspected, unexpected, serious adverse reaction
$t_{1/2}$	plasma half-life
TB	total bilirubin
TEAE	treatment emergent adverse event(s)
$T_{max}$	time to maximum concentration
UDCA	ursodeoxycholic acid
ULN	upper limit of normal

## PROTOCOL SYNOPSIS

Sponsor: Enanta Pharmaceuticals, Inc.
Name of Investigational Product: EDP-305
Study Title: A Phase 2 Dose Ranging, Randomized, Double Blind, Placebo-Controlled Study Evaluating the Safety, Tolerability, Pharmacokinetics and Efficacy of EDP-305 in Subjects with Primary Biliary Cholangitis (PBC) with or without an Inadequate Response to Ursodeoxycholic Acid (UDCA)
Protocol Number: EDP 305-201
Phase of Development: 2
Study Centers: The study will be conducted at approximately 65 sites located in both the US as well as international locations.
Number of Subjects Planned: Approximately 119 subjects will be enrolled.
Investigational Product, Dosage, and Mode of Administration: EDP-305 will be supplied as 1mg and 2.5mg tablets for oral administration; doses administered will be 1 mg, 2.5 mg, or placebo taken once daily (QD) for 12 weeks.
Duration of Treatment: 12 weeks.
Objectives: Primary Objective: 

To evaluate the effect of EDP-305 on alkaline phosphatase (ALP) levels.

 Secondary Objective: 

To evaluate the safety and tolerability of EDP-305

To evaluate the effect of EDP-305 on bilirubin levels

To evaluate the effects of EDP-305 on other markers of liver function

To evaluate the effects of EDP-305 on non-invasive markers of liver fibrosis

To evaluate the effects of EDP-305 on inflammatory markers

To evaluate the effects of EDP-305 on lipids

To evaluate the effects of EDP-305 on pruritus

To evaluate the effects of EDP-305 on Quality of Life (QoL)

To evaluate the pharmacokinetics (PK) of EDP-305 and metabolites in plasma

To evaluate the pharmacodynamics (PD) of EDP-305

Criteria for Evaluation: Primary Endpoint: 

Proportion of subjects with at least 20% reduction in ALP from pretreatment value or normalization of ALP at Week 12

 Secondary Endpoints: 

Frequency of adverse events (AEs), serious AEs, and AEs leading to discontinuation through Week 12

- Bilirubin (Total, Conjugated, Unconjugated) decline from Baseline at Week 12
- Change from Baseline in Alanine aminotransferase (ALT) and Aspartate aminotransferase (AST), Gamma-Glutamyl transferase (GGT) at Week 12
- Change from Baseline of noninvasive liver fibrosis markers (Enhanced Liver Fibrosis [ELF] panel, PRO C3, AST to Platelet Ratio Index [APRI] and fibrosis-4 [FIB-4]) at Week 12
- Change from Baseline in fibrinogen, CRP, IL6, IL1 $\beta$ , TNF- $\alpha$ , TNF- $\beta$ , alpha2 macroglobulin and haptoglobin levels at Week 12
- Change from Baseline in Triglycerides (TG), Total Cholesterol (TC), High Density Lipoprotein Cholesterol (HDL-C), Low Density Lipoprotein Cholesterol (LDL-C) at Week 12
- Change from Baseline in 5D-itch scale and Visual Analog Score (VAS) at Week 12
- Change from Baseline in PBC-40 Quality of Life (QoL) at Week 12
- Pharmacokinetic parameters of EDP-305 (and metabolites):  $C_{max}$ ,  $T_{max}$ , and  $AUC_{last}$ .
- Pharmacodynamic parameters of EDP-305: FGF19, C4 and Bile Acid (BA) at Week 12

**Study Design:**

This is a multicenter, double blind, placebo controlled, dose ranging Phase 2 study assessing the safety and efficacy of two doses of orally administered EDP-305. The total maximum length of time for participation for each subject enrolled in the study will be approximately 20 weeks. The study will consist of a Screening Period, Treatment Period and a Follow-up Period as shown in the following table.

Study Period	Duration
Screening	Up to 4 weeks (28 Days)
Treatment	12 weeks
Follow-up	4 weeks
Total approximate maximum duration of participation	up to 20 weeks

Screening Period: After reviewing and signing the Informed Consent Form (ICF), subjects will be screened and must meet all criteria for entry into the study. The Screening Visit must occur between Days -28 and -1 (up to 4 weeks). All Screening assessments must occur within the -28 to -1 window.

[figure not shown]
Treatment Period: Subjects who have met all study criteria will report to the site on the morning of Day 1. Subjects must have fasted for at least 8 hours prior to dosing. Subjects will be randomized in a 3:3:1 manner to receive one of two doses of EDP-305 or placebo QD. Procedures performed are specified in the Schedule of Assessments (Appendix 1). Predose assessments will be conducted (including laboratory sample collection) before the subject

receives the first dose of study drug in the clinic. Following dosing, PK and biomarker samples will be collected. Prior to leaving the clinic on Day 1, study drug will be dispensed to the subjects and the subjects will be given instructions for taking study drug at home. Subjects will take study drug once daily for a total of 12 weeks returning to the clinic for efficacy and safety assessments on Day 3 and Weeks 2, 4, 8 and 12. On study days when there is a clinic visit, subjects will be administered their daily dose in the clinic. Additional PK and PD samples will be collected over a period of 8 hours on Day 1 and Week 12 (Day 84/End of Treatment, [EOT]) from subjects at a subset of sites that have the technical capability to collect and process intensive (longer duration) PK and PD samples (PK/PD Sub-study).

***Safety Follow-up and Early Termination Visit:*** The safety follow-up visit (or End of Study [EOS] visit) will occur 4 weeks after the last dose of study drug for all subjects, including those who discontinue treatment early (ie, prior to completing 12 weeks of dosing). Final study assessments will be completed at that visit.

Subjects who discontinue treatment early should return to the clinic as soon as possible following the last dose of study drug for an EOT visit. They should then return for the EOS visit 4 weeks following last dose of study drug.

### Study Design:

Abbreviations: D=Day; W=Week

### Eligibility Criteria:

#### ***Inclusion Criteria***

*Subjects must meet all of the following criteria to be eligible to participate:*

1. An informed consent document must be signed and dated by the subject
2. Male and female subjects of any ethnic origin between the ages of 18 and 75 years, inclusive
3. Male or female with a diagnosis of PBC by at least two of the following criteria:
  - History of ALP above ULN for at least 6 months

- Positive Anti-Mitochondrial Antibodies (AMA) titers ( $>1/40$  on immunofluorescence or M2 positive by enzyme linked immunosorbent assay [ELISA] or positive PBC-specific antinuclear antibodies [PBC- ANAb])
  - Documented liver biopsy result consistent with PBC (with no cirrhosis)
4. For subjects with no documented liver biopsy performed within 2 years, subjects must undergo a transient elastography (Fibroscan) showing liver stiffness  $<14.0$  kPA
  5. Must be on a stable dose of UDCA  $12-20$  mg/kg/day for at least 6 months prior to Screening or intolerant of UDCA in the opinion of the Investigator (no UDCA for at least 12 weeks prior to Screening)
  6. Alkaline Phosphatase (ALP)  $\geq 1.67 \times$  ULN and/or total bilirubin  $>ULN$  but  $<2 \times$  ULN ( $<2.4$  mg/dL)
  7. Subjects must have Screening laboratory values for Hepatitis B surface antigen (HBsAg), anti-HCV antibodies and HCV RNA negative, and Human Immunodeficiency Virus (HIV) 1 and 2 antibodies (Ab) as seronegative. NOTE: Subjects previously infected by chronic hepatitis C and treated with direct acting antivirals (DAAs) with sustained virologic response (SVR) for at least 3 years will be allowed.
  8. Female subjects of childbearing potential must agree to use two effective methods of contraception from the date of Screening until 90 days after the last dose of EDP-305. Effective methods of contraception are defined as:
    - a condom for the male partner and at least one of the following for the female participant:
      - Intrauterine device
      - Oral, injectable, implantable, transdermal, or intravaginal hormonal contraceptiveNote: The above does not apply to female subjects of non-childbearing potential (ie, physiologically incapable of becoming pregnant) defined as:
    - has had a complete hysterectomy greater than or equal to 3 months prior to dosing or
    - has had a bilateral oophorectomy (ovariectomy) or
    - has had a bilateral tubal ligation or fallopian tube inserts or
    - is postmenopausal (a demonstration of a total cessation of menses for  $\geq 1$  year with an FSH level of  $>35$  mIU/mL).
  9. All male participants who have not had a vasectomy must use effective contraception from Day -1 to 90 days after their last dose of study drug. Effective contraception is defined as a condom and spermicide for the male, or condom and at least one of the following for a female partner:
    - Intrauterine device
    - Oral, injectable, implantable, transdermal, or intravaginal hormonal contraceptive
    - Be of non-childbearing potential
  10. Male subjects must agree to refrain from sperm donation from the date of Screening until 90 days after their last dose of study drug
  11. Screening body mass index (BMI) of  $\geq 18$  kg/m^2
  12. Subject must be willing and able to adhere to the assessments, visit schedule, prohibitions and restrictions, as described in this protocol

### ***Exclusion Criteria***

*Subjects who meet any of the following criteria will not be eligible to participate:*

1. Laboratory Screening Results:
  - AST  $>5 \times$  ULN

- ALT  $>5 \times$  ULN
  - Patients with Gilbert's syndrome will not be allowed due to interpretability of bilirubin levels
  - Total white blood cells (WBC)  $<3000$  cells/mm^3
  - Absolute neutrophil count (ANC)  $<1500$  cells/mm^3
  - Platelet count  $<140,000$ /mm^3
  - Prothrombin time (international normalized ratio, INR)  $>1.2$
  - Serum creatinine  $>2$  mg/dL or creatinine clearance  $<60$  mL/min (based on Cockcroft-Gault Method)
2. Suspected to have relevant nonalcoholic fatty liver disease (NAFLD) as based on the judgment of the Investigator at Screening
  3. Known history of alpha-1-Antitrypsin deficiency
  4. Use of immunosuppressants known to have an effect on the liver of patients with PBC (eg, colchicine, methotrexate, or azathioprine) in the 3 months preceding Screening.
  5. Current use of fibrates, including fenofibrates. NOTE: Subjects who discontinued fibrates for at least 3 months before Screening can participate
  6. Use of an experimental treatment for PBC within the past 6 months
  7. Prior use and/or concomitant treatment with obeticholic acid (OCA)
  8. Use of experimental or unapproved drugs within 1 year of Screening
  9. Any other condition(s) that would compromise the safety of the subject or compromise the quality of the clinical study, as judged by the Principal Investigator (PI)
  10. Pregnant or nursing females
  11. Recipients of liver or other organ transplantation or anticipated need for orthotropic organ transplantation in one year as determined by a Model for End-Stage Liver Disease (MELD) Score  $\geq 15$
  12. Co-existing liver or biliary diseases, such as primary sclerosing cholangitis, choledocholithiasis, acute or chronic hepatitis, autoimmune hepatitis, alcoholic liver disease, nonalcoholic steatohepatitis (NASH), acute infection of bile duct system or gall bladder, history of gastrointestinal bleeding (secondary to portal hypertension), cirrhosis, cholangiocarcinoma diagnosed or suspected liver cancers
  13. Cirrhosis with or without complications, including history or presence of: spontaneous bacterial peritonitis, hepatocellular carcinoma
  14. Hepatorenal syndrome (type I or II) or Screening serum creatinine  $>2$  mg/dL (178  $\mu$ mol/L)
  15. Prior variceal hemorrhage, uncontrolled encephalopathy, Child-Pugh Class A, B and C, esophageal varices, or refractory ascites within the previous 6 months of Screening (defined as date informed consent signed)
  16. Patients with a history of severe pruritus requiring current or prior systemic treatment (e.g., with BAS or rifampicin)
  17. Medical conditions that may cause nonhepatic increases in ALP (e.g., Paget's disease)
  18. Any condition possibly affecting drug absorption (eg, gastrectomy  $<3$  years prior to Screening. NOTE: Subjects who have undergone gastric surgeries known to not affect drug absorption such as gastric band or gastric sleeve will be allowed if they are stable for at least 1 year prior to Screening.
  19. History of regular alcohol consumption exceeding 14 drinks/week for females and 21 drinks/week for males within 6 months of Screening. One drink is defined as 5 ounces

(150 mL) of wine or 12 ounces (360 mL) of beer or 1.5 ounces (45 mL) of hard liquor)

20. Participation in a clinical trial within 30 days prior to study drug administration
21. Clinically significant electrocardiogram (ECG) abnormalities or QTcF greater than 450 ms for males and 470 ms for females at either Screening or Baseline, or any prior history of QT abnormality
22. Use of CYP3A4 and P-gp inducers and inhibitors within 14 days prior to the first dose of study medication and throughout study duration
23. Clinically significant history of drug sensitivity or allergy, as determined by the PI
24. Subject has received an investigational agent or investigational vaccine within 30 days, or a biological product within 3 months or 5 elimination half-lives (whichever is longer) prior to the planned intake of study drug
25. Use of a new statin regimen from Screening and throughout study duration.  
NOTE: Subjects on a stable dose of statins for at least 3 months prior to Screening are allowed. No dose modification during the study will be allowed.
26. Use of immunosuppressants (eg, systemic corticosteroids) for more than 2 consecutive weeks in duration within 1 year prior to Screening.

**Subject Withdrawal:**

Subjects may choose to discontinue from the study at any time. Subjects may also be discontinued from the study at any time if the subject, Investigator or Sponsor determines that it is not in the best interest of the subject to continue participation. Subjects who prematurely withdraw from the study for any reason after having been randomized will not be replaced. Subjects who prematurely discontinue treatment early and received at least one dose of study drug should return to the clinic as soon as possible to complete the EOT Visit and for the Safety Follow-up Visit 4 weeks after their last dose.

Individual subjects who meet the following Stopping Rules will be discontinued from further dosing and thorough evaluation and follow-up will be performed:

- If ALT or aspartate aminotransferase (AST) increases to  $>5 \times$  Baseline.
- If ALT or AST increase  $>2 \times$  Baseline AND the increase is accompanied by a concomitant total bilirubin (TB) increase  $>2 \times$  Baseline OR the INR concomitantly increases by  $>0.2$
- If elevations of ALT/AST are accompanied by signs or symptoms of right upper quadrant abdominal pain, anorexia, nausea, vomiting fever, eosinophilia, and/or rash.

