#### **7.1.4 Treatment Period Visits (Day 3, Weeks 2, 4, 8 and 12 /EOT)**

Except for days when there is a clinic visit, subjects will take their daily dose of study drug at home for 12 weeks. Throughout the 12-week treatment period, subjects will return to the clinic as shown in the SoA (Appendix 1) for study assessments. Prior to each visit, subjects will be instructed to fast for a minimum of 8 hrs prior to the scheduled visit time.

At the end of the treatment period, subjects will complete the EOT visit. Subjects who complete 12 weeks of treatment will complete the EOT assessments at the Day 84 visit/Week 12. Subjects who discontinue treatment early should complete EOT assessments at the time of discontinuation (if in the clinic) or as soon thereafter as possible if the subject discontinues treatment while not in the clinic. Procedures performed are specified in the SoA (Appendix 1).

Population PK and PK/PD samples will be collected as specified in the SoA (Appendix 1) and as described in Section 8.4.

Subjects should discontinue drug on Day 84. Subjects, who return for their EOT Visit after Day 84, should stop dosing on Day 84 (Week 12 Visit).

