### 10.1 Individual Subject Stopping Rules

Study drug will be discontinued in subjects with elevated ALT or AST (see below) and thorough evaluation and follow-up will be performed:

- If ALT or AST increases to  $>5 \times$  Baseline.
- If ALT or AST increase  $>2 \times$  Baseline AND the increase is accompanied by a concomitant TB increase to  $>2 \times$  Baseline OR the INR concomitantly increases by  $>0.2$
- If elevations of ALT/AST are accompanied by signs or symptoms of right upper quadrant abdominal pain, anorexia, nausea, vomiting, fever, eosinophilia, and/or rash.

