6.3 Study Day Windows

The windows for all visits including PK draws appear in table below:

Visit	Target Day	Time window
Screening	Day -1	Day -28 to Day -1
Day 1	Day 1	N/A
Day 3	Day 3	N/A
Week 2	Day 14	Day 4 to Day 21
Week 4	Day 28	Day 22 to Day 42
Week 8	Day 56	Day 43 to Day 70
Week 12	Day 84	Day 71 to less than or equal to End of Treatment+7 days
Treatment-Free Follow-up Week 4	Day 112	Greater than End of Treatment+7 days to last visit

- Samples at each visit should be obtained at different times postdose relative to each of the other visits (2, 4, and 8)
- The target day for the screening visit is Day -1 during the period of Day -28 to Day -1

The relative day will be computed for each laboratory, vitals, ECG and PD data point. The relative day will be calculated as visit date-date of first dose+1. For data collected prior to first dose, the relative day will be calculated as visit date-date of first dose. When there are multiple observations within a visit window, the value closest to the target day will be analyzed..

PK/PD Draw Timing

Visit	Target Day	PK/PD Substudy (PK, C4, FGF19, BA, and additional ALP samples)	Population	
			For subjects not substudy	
			PK	PD (FGF19, BA, C4)
Day 1	Day 1	At predose and 2, 6, and 8 hr postdose	at predose and two samples postdose; 
 • First sample collected 1 to 3 hours postdose • Second sample at least 1 hour later 	At predose
Week 2	Day 14	at predose and two samples postdose; 
 • First sample collected 1 to 3 hours postdose • Second sample at least 1 hour later 	at predose and two samples postdose; 
 • First sample collected 1 to 3 hours postdose • Second sample at least 1 hour later 	At predose
Week 4	Day 28	at predose and two samples postdose; 
 • First sample collected 1 to 3 hours postdose • Second sample at least 1 hour later 	at predose and two samples postdose; 
 • First sample collected 1 to 3 hours postdose • Second sample at least 1 hour later 	At predose
Week 8	Day 56	at predose and two samples postdose; 
 • First sample collected 1 to 3 hours postdose • Second sample at least 1 hour later 	at predose and two samples postdose; 
 • First sample collected 1 to 3 hours postdose • Second sample at least 1 hour later 	At predose

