9.1.3 Imputation of Missing Data

To account for missing data, a sensitivity analysis will be performed using the multiple imputation Markov Chain method.

MMRM Using Multiple imputation (MI)

To assess robustness of the efficacy analysis, sensitivity analysis with missing values imputed by MI will be performed on ALP change from baseline data. In the first stage, missing values will be imputed by Markov Chain Monte Carlo (SAS PROC MI, MCMC) to make the missing pattern monotone (by filling in

imputed values of ALP between 2 non-missing values). In the second stage, monotone linear regression will fill in missing values through Week 12. SAS PROC MI and PROC MIXED will be used to obtain MMRM estimates of treatment difference. SAS PROC MIANALYZE will be used to combine estimates and to generate the average test statistics for hypothesis testing. The Missing at Random method will be used with the following parameters MAR – assume missing at random, number of imputation=100, seed=SEED11 (for MCMC) and SEED12 (for MONOTONE REG) for imputation.

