9.2.1.2 Alanine Aminotransferase

A descriptive summary will be provided for ALT values, change from Baseline and percentage change from Baseline using 8-number summary by visit and treatment group.

Change from Baseline and percentage change from Baseline at week 12 will be analyzed using an ANCOVA model with treatment as fixed effect and the associated baseline value as covariate. Least squares means and standard errors will be presented for each visit, p-value and 2-sided 95% confidence interval for treatment differences will be presented for each visit. Significance tests will be based on least-squares means using a two-sided $\alpha = 0.05$.

A by-subject listing will be provided for observed and derived variables.

Mean \pm SD and change from baseline for ALT values by visit and treatment group will be plotted.

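### Subjects stopped early for ALT or AST rises drop out of the Week 12 ALT, AST and bilirubin comparisons, which may bias them in a direction set by how the stops fall between arms

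*Protocol*

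**What the plan says.** **Stopping rules.** The synopsis, under Subject Withdrawal, says: "Individual subjects who meet the following Stopping Rules will be discontinued from further dosing and thorough evaluation and follow-up will be performed". Protocol 10.1 opens: "Study drug will be discontinued in subjects with elevated ALT or AST (see below) and thorough evaluation and follow-up will be performed". There are three rules:
- ALT or AST above 5 times Baseline.
- ALT or AST above 2 times Baseline with a second condition, either bilirubin ("AND the increase is accompanied by a concomitant TB increase to" more than 2 times Baseline) or an INR rise above 0.2.
- A symptom rule with no minimum size of rise: "If elevations of ALT/AST are accompanied by signs or symptoms of right upper quadrant abdominal pain", or other listed symptoms.

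**Visits after stopping.** Protocol 7.1.4: "Subjects who discontinue treatment early should complete EOT assessments at the time of discontinuation (if in the clinic) or as soon thereafter as possible". The only other visit is the End of Study visit, 4 weeks after the last dose (Protocol 7.1.5 and 7.2). No off-drug Day 84 visit is planned.

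**Endpoints and analysis.** Week 12 change in ALT, AST and bilirubin are secondary endpoints (Protocol 2.2.2). For ALT, SAP 9.2.1.2 says: "Change from Baseline and percentage change from Baseline at week 12 will be analyzed using an ANCOVA model with treatment as fixed effect", with baseline as covariate. AST and bilirubin are handled in the same way.

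**Windows.** SAP 6.3 places laboratory values by day relative to first dose. Week 12 is "Day 71 to less than or equal to End of Treatment+7 days", and later samples belong to follow-up.

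**Missing data.** Counting a missing value as failure applies to the ALP response only (SAP 9.1.1). Imputation is also confined to ALP (SAP 9.1.3): "sensitivity analysis with missing values imputed by MI will be performed on ALP change from baseline data". No rule is given for ALT, AST or bilirubin.

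**The concern.** The same measurement serves as an endpoint and as a reason to stop drug. When a stop occurs early enough, the subject is missing from the Week 12 comparison because of recorded values of that endpoint. The same subject, with ALP from the same chemistry panel, counts as a non-responder in the primary analysis.

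At stake is whether the Week 12 ALT, AST and bilirubin differences describe everyone treated or only those who reached Week 12 without a liver stop. With 45 subjects per active arm and 15 on placebo, one or two subjects can matter.

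**Working it through.** The plan gives no figure on this point, so there is none to reproduce.

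**1. Who loses the Week 12 value.** The window runs from Day 71 to end of treatment + 7. It is empty when end of treatment + 7 < 71, that is, when treatment ends before Day 64.
- Stop at Day 3, Week 2 or Week 4: no Week 12 value.
- Stop at Week 8 (Day 56 ± 2, so Day 54 to 58): end of treatment + 7 is Day 61 to 65, before Day 71. No Week 12 value.
- Stop from Day 64 on: a Week 12 value exists only if a sample is taken on or after Day 71.
- Rise first found at Week 12: stays in.

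The early end-of-treatment sample falls in the window of the day on which it was drawn, and the End of Study sample falls in follow-up.

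**2. Size.** Arm sizes of 45 and 15 are from Protocol 11.2. Everything else is assumed, because the documents give no stop rate and no SD: a true ALT ratio of 0.82 on active, no change on placebo, and a log-scale SD of 0.25.

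Mean percent change without stops, using exp(0.25²/2) = 1.0317:
- Active: 0.82 × 1.0317 − 1 = −15.4%
- Placebo: 1.0317 − 1 = +3.2%
- Difference: −18.6 points

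If *k* active subjects are kept in at *x* times Baseline instead of dropped:
- shift in the active mean = k × [100(x − 1) + 15.4] / 45
- geometric ratio = 0.82 × exp{k × [ln x − ln 0.82] / 45}

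| Value carried | Stops on active | Shift (points) | Difference (points) | Geometric ratio |
|---|---|---|---|---|
| 2x | 1 | 2.6 | −16.0 | 0.84 |
| 2x | 2 | 5.1 | −13.4 | 0.85 |
| 3x | 1 | 4.8 | −13.8 | 0.84 |
| 3x | 2 | 9.6 | −9.0 | 0.87 |
| 5x | 1 | 9.2 | −9.3 | 0.85 |
| 5x | 2 | 18.5 | −0.1 | 0.89 |
| 6x | 1 | 11.5 | −7.1 | 0.86 |
| 6x | 2 | 22.9 | +4.3 | 0.90 |

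If stopped subjects are instead back at an untreated level by Week 12, the shift is (3.2 + 15.4)/45 = 0.4 points for one and 0.8 for two.

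**3. Direction.** Same model, stops carried at 5x:
- One placebo stop raises the placebo mean by (400 − 3.2)/15 = 26.5 points. The difference with everyone kept is −45.0, so dropping that subject understates benefit.
- Three active stops and one placebo stop (equal rates at 3:1): 3 × 415.4/45 − 26.5 = 27.7 − 26.5 = +1.2 points. The difference is −17.3, close to −18.6.

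**4. What an MMRM recovers.** Assume equal correlation ρ between visits, a raised value only at the last of *j* attended visits, and a rise that would persist to Week 12. The MMRM then carries the fraction ρ / [1 + (j − 1)ρ] of the excess forward. At ρ = 0.6, stops at Week 2, 4 and 8 (j = 1, 2, 3) give 0.60, 0.375 and 0.27, with mean 0.42. The means at ρ = 0.4 and 0.8 are 0.30 and 0.52. A simulation of 1,500 trials per case (45 vs 15, stops at 6x, week chosen at random) gave 0.31, 0.41 and 0.52. At ρ = 0.6 with two stops, the ratio was 0.82 from observed values only, 0.85 from the MMRM and 0.90 with all values retained.

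**The case against.** **Direction is not established.** A reader might infer that a liver benefit is overstated. That needs stops to be proportionally more frequent or larger on EDP-305, and the documents do not show this. The one earlier ALT/AST discontinuation they report was at 20 mg (Protocol 1.4.1), whereas this trial uses 1 and 2.5 mg. Steps 2 and 3 show bias in either direction or almost none. This objection stands.

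**The largest shifts need strong inputs.** A reader might also infer that two stops reverse the sign. At 5x, two stops leave the difference at −0.1. It turns positive only with values near 6x, carried unchanged to Week 12, on raw percent change, while the log-scale ratio stays below 1. A sign reversal is therefore not a finding.

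**The rules do not remove the whole upper tail.** Bilirubin never stops drug alone. Rises between 2 and 5 times Baseline without raised bilirubin, raised INR or symptoms stay in. The symptom rule can remove small rises.

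**The rises are not hidden.** Least-squares means are planned at each visit, and SAP 10.2.1 counts the stopping categories by treatment group. That is correct, and triggering values can enter earlier-visit results. Neither output changes the Week 12 estimate, however, and the counts sit among the safety outputs.

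**Exclusion is inferred.** The SAP does not say that only observed values are used. The schedule of assessments has one column for End of Treatment and Week 12, so early samples might have been meant to count as Week 12. SAP 6.3 points the other way, and the SAP should settle it.

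**Conclusion.** The gap is real. Following SAP 6.3 and 9.2.1.1 to 9.2.1.3 as written, a subject stopped under the liver rules before about Day 64 leaves the Week 12 ALT, AST and bilirubin comparisons, with no rule for the missing value. The case is strongest for ALT and AST; bilirubin is affected only jointly with them.

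The result may be biased: towards EDP-305 if stops are proportionally more frequent or larger on active, by about zero if balanced, and against EDP-305 if more frequent on placebo. Under the assumed inputs, one or two active stops carried at 5 to 6 times Baseline shift the active mean by about 9 to 23 points, or move the ratio from 0.82 to between 0.85 and 0.90. Stops at 2 to 3 times shift it by about 3 to 10 points, and a return to an untreated level by less than 1. The actual size depends on the number of stops and on which value is meant to represent a stopped subject, and the plan states neither.

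These are secondary endpoints in a Phase 2 trial, and the remedy is cheap. It should be made, but it does not touch the primary analysis.

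**What to change.** In SAP 9.2.1.1 to 9.2.1.3:

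1. Replace the Week 12 ANCOVA with an MMRM on the log scale. Use all on-treatment values, including early end-of-treatment values, with treatment-by-visit and baseline-by-visit terms, and read the contrast at Week 12. Missing at random is a reasonable working basis where a stop depends on recorded values.
2. Because the MMRM corrects only part of the bias if rises persist (about 30% to 50% in the check above), add a sensitivity analysis that takes the early end-of-treatment value as the Week 12 value.
3. Show the liver-rule stop counts by arm, already planned in SAP 10.2.1, beside the Week 12 results.

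Cost: SAP wording and modest programming. The values are already collected, and PROC MIXED is already planned for ALP. The price is a missing-at-random assumption and estimates that may look less favourable. GGT triggers no stop and is left out. No change to the stopping rules is proposed.
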